Introduction and rationale During Total Knee Arthroplasty (TKA), the joint is subjected to considerable stress, which has been shown to be related to a recruitment and activation deficit of the quadriceps femoris muscle. The explanation for this correlation lies in a complex mechanism called Arthrogenic Muscle Inhibition (AMI). So far, AMI has been directly studied only in sub-acute and chronic phase after TKA because of the invasive procedures employed in order to evaluate it; However, clinical observation and some experimental studies also suggest the presence of this phenomenon in the initial postoperative days. The aim of the study is to investigate possible differences in quadriceps muscular activity, which could be associated with AMI and which may be investigated in the acute phase; data acquisition will be made on the first and third days after surgery.

Population and selection criteria 15 healthy subjects and 15 patients on hold for TKA will be recruited between July and September 2019. The inclusion criteria will be: age greater than 18 years old and a recent TKA or revision of TKA. Those patients with arthrogenic muscle inhibition before TKA with QAB<6 and the subjects with conditions (other than those which led to the TKA) that could interfere with quadriceps muscle activation or with motor performance will be excluded from the study.

Design and duration Prospective observational study. It will start in July 2019 and the recruitment period should last until September 2019.

Aims The primary aim of this study is the evaluation of possible differences in quadriceps muscular activation after TKA. Subjects will be asked to perform different tasks in isometric contraction, keeping the biomechanical context constant. Secondly, the correlation between the primary aim and the pain referred by the patient, registered using the NRS scale, will be investigated along with the patient's functional ability, assessed by means of the Timed Up and Go Test (TUG). There will be three assessment sessions: the day prior to the TKA procedure and at one and three days postoperatively.

Statistical methods and data analysis

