At the end of data acquisition, the normality and homogeneity of the demographic variables will be assessed, as will the outcome measures at baseline. Differences in the outcome measures will be investigated with the t student test (or with the related non-parametric tests) and by means of the mixed models repeated measures ANOVA test. Linear regression will be applied so as to evaluate the correlation between outcomes.

Ethical considerations

The study population will comprise subjects who have undergone TKA; they will be assessed in isometric contractions of quadriceps femoris in the acute phase after surgery. It is assumed that this type of evaluation does not lead to adverse events, since in terms of demands made on muscle and joints, it is comparable with the physiotherapeutic treatment administered to all patients twice a day after TKA. The aim of this study is to understand how the quadriceps activates in acute phase after TKA in order to identify the best physiotherapeutic approach for the initial postoperative days. Data acquisitions will be made so as to allow the patients to participate in both physiotherapy sessions.

For the study, the materials supplied to the Movement Analysis Laboratory of the Humanitas Clinic will be used. Each assessment session will last about 20 minutes.

Timing of the study

Recruitment of subjects: July– September 2019

Data analysis: September - October 2019

Report presentation: November 2019

2 Background and introduction

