Total Knee Arthroplasty is currently considered an effective treatment in reducing pain, improving functional abilities and quality of life in patients with advanced-stage knee osteoarthritis and in other diseases affecting the knee joint [1] [2]. However, considering that TKA is recognised as major surgery, the knee joint is subjected to considerable stress. This has been shown to be related to a recruitment and activation deficit of the quadriceps femoris muscle, both in sub-acute phase (starting from two weeks after surgery) and chronic phase (up to one year if compared with the contralateral limb) [3] [4] [5] [6]. This complex mechanism is termed arthrogenic muscle inhibition (AMI), properly defined as the long-lasting inability to fully activate the quadriceps muscle in the absence of nerve damage, following surgery and/or traumatic injury of the knee joint [7]. Although AMI has to date been described only in sub-acute and chronic phase after TKA because of the invasive procedures employed in order to evaluate it, some researchers have investigated this phenomenon by inducing in healthy subjects the same symptoms which are characteristic of the immediate postoperative period following knee surgery. These studies report a positive correlation; in particular they have shown how, inducing inflammation, pain and increasing intra-articular pressure, a recruitment deficit of the quadriceps muscle arises [8] [9] [10]. Clinical practice and published scientific research indicate the presence of AMI also in the acute phase after TKA.

3 Rationale

For ethical reasons, there are no studies currently published that directly investigate the presence and the size of AMI in the initial postoperative days following TKA. Clinical practice, and the study of AMI in sub-acute patients and in experimental clinical conditions, indicate an activation deficit of the quadriceps from the first day following surgery. This study aims to evaluate the role that AMI could play in the postoperative acute phase after TKA, examining possible differences in the activation patterns of the quadriceps muscle between patients and healthy subjects.

The results could be useful to better manage the treatment of patients affected by a recruitment deficit of quadriceps muscle, by reducing motor impairment and by improving the quality and precision of the physiotherapy in the acute phase after TKA.

4 Aims

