4.1 General aims

The objective of the study is to evaluate possible differences in quadriceps muscular activation after TKA during the acute phase, with a comparison with healthy subjects. Moreover, it will be investigated whether any correlation exists between the outcomes obtained, the pain reported by the patient and his or her functional ability.

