4.2 Endpoints

4.2.1 Primary endpoint

The primary aim is to observe possible activation alterations of the quadriceps femoris, more specifically of the vastus medialis, lateralis and rectus femoris muscles, by means of electromyographic signal acquisition. The subject will be asked to perform different tasks in isometric contractions, without changing the biomechanical context. The subjects will be asked to perform a homolateral knee extension, a homolateral hip flexion, a contralateral hip extension with

a contemporary homolateral hip flexion. The activation of the three muscles will be recorded through surface electromyography (sEMG) with four channels (FREEEMG 1000, BTS SpA). The electromyographic surface sensors will be positioned following the European SENIAM guidelines regarding vastus medialis, lateralis and rectus femoris of quadriceps femoris homolateral in terms of surgery access, in order to evaluate the activation intensity during the different tasks [11].

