6.1 General design

The patients scheduled for TKA will be recruited through the criteria mentioned above; moreover, healthy subjects will be recruited as control group. The patients will be assessed through a motor ability test (TUG), a referred pain scale, and a quadriceps isometric contractions session recorded with surface electromyography. The assessment sessions will be conducted the day before the operation and on the first and third postoperative day. The control group will be exposed once to the same assessments, with the EMG applied on the quadriceps muscle of the dominant limb.

The sEMG data will be acquired by asking the subjects to perform the following tasks: "homolateral knee extension", "homolateral hip flexion" and "contralateral hip extension with a contemporary homolateral hip flexion". Each task will be repeated twice and the execution order will be randomized. The subject will be placed in the supine position and three bands will be positioned respectively at the level of the malleolus and the inferior margin of the patella in order to immobilise the inferior limb and ensure an isometric contraction of the quadriceps, while keeping

the biomechanical context unchanged. For each subject belonging to the two study groups, the same setting will be used. During the data acquisitions, every subject will be encouraged to perform each contraction with the maximum strength. The performance of tasks will be video recorded in order to monitor the correct execution.

The NRS scale will be administered to the patients after each quadriceps evaluation session, while the TUG test will be conducted the day before the operation and on the third day after surgery.

In the first and third day after surgery, the session will take place after 3pm in order to allow the patients to participate in both of the physiotherapeutic treatments provided by the Humanitas Clinic Institute.

The TUG test consists in asking the patient to stand up from a chair, walk at spontaneous speed, turn back at a cone placed at a distance of 3 metres and sit back down on the chair. The patient will be timed starting from the operator mark and stopping when the patient has resumed the seated position on the chair. The test will be performed once in a session, with a mock test before.

The NRS scale consists of one 10cm segment, numbered from 0 to 10 on which the subject has to quantify their pain perception where 0 equals “no pain” and 10 equals “the worse pain ever perceived”.

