7.2 Analysis

The statistical analysis will be carried out at the end of the data collection, using the SPSS 20.0 software. The categorical variables will be described via mean and standard deviation or median and interquartile range. The normality of the demographic variables and the outcome measures will be evaluated through the Kolmogorov-Smirnov test.

The t Student test (with normal variables) or the Mann-Whitney test (with non-normal variables) will be used to verify the pre-intervention homogeneity of the demographic variables. The mixed models ANOVA test for repeated measures will be used to analyse possible differences inter-groups and intra-groups. A post hoc analysis will be conducted in the eventuality of significant outcomes. Linear regression will be used to investigate the correlation between the EMG outcomes and the secondary outcomes (NRS and TUG).

The threshold value for the statistical significance will be fixed at 0.05.

8 Withdrawal from the study

Subjects who decide to leave the study for any reason will be immediately excluded from it. The subjects will be also informed about the possibility of withdrawal from the study at every session provided for by the protocol, including during the planned follow-up period, giving prior notification to any of the experimenters. Data acquired from those subjects who do not complete the study will be excluded from the analysis.

9 Forms and procedures for the data collection and management

The demographic and outcome data will be input into an anonymous form within an Excel sheet (*Attachment B*). This data will be collected by two experimenters in order to minimise any errors and will be saved in password-protected electronic format.

10 Ethical considerations

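### The patient-versus-healthy comparison of EMG level is open to confounding, mainly by age: the visible text neither aligns controls with patients nor names a covariate

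*Combined protocol and SAP*

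**What the plan says.** Section 4.1 sets the objective as quadriceps activation after TKA "during the acute phase, with a comparison with healthy subjects". Section 3 approaches the role of arthrogenic inhibition by "examining possible differences in the activation patterns of the quadriceps muscle between patients and healthy subjects". Section 4.2.1 places the sensors "in order to evaluate the activation intensity during the different tasks". Section 7.1 justifies the sample by a preliminary look at differences between groups.

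On who is compared, the synopsis says "15 healthy subjects and 15 patients on hold for TKA will be recruited between July and September 2019". Section 6.1 adds only that healthy subjects form the control group and attend once, with EMG on the dominant limb. Section 4.2.1 puts the patients' sensors on the operated side. The only age criterion, in 5.1, is a minimum of 18 years. Attachments A and B are not shown, so a recruitment rule placed there cannot be excluded.

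On analysis, 7.2 states: "The mixed models ANOVA test for repeated measures will be used to analyse possible differences inter-groups and intra-groups". No covariate is listed, although 10.2 says that age and sex are collected. A t or Mann-Whitney test "will be used to verify the pre-intervention homogeneity of the demographic variables". The synopsis is slightly wider: "the normality and homogeneity of the demographic variables will be assessed, as will the outcome measures at baseline". Neither place says what follows if the groups differ.

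**The concern.** Patients and volunteers are not randomised to their groups, so a difference in EMG level mixes the effect of the knee and the surgery with any other way in which the two groups differ. Age is the main candidate. One group is defined by eligibility for TKA, and the other may be any adult over 18. The limb rule also differs by group.

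An age-related difference in level could be read as part of the activation deficit that the study looks for. More subjects recruited in the same way would not remove it. The patients' pre-operative session protects their own change over time, but that change does not show how far patients are from healthy activation. Controls attend once, so that distance rests wholly on the unprotected contrast.

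**Working it through.** The plan has no figure to reproduce: 7.1 says that a sample size cannot be calculated and gives no effect size, SD or power.

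**Inputs from the documents.** 15 patients and 15 controls (7.1); threshold 0.05 (7.2; sidedness is not stated, two-sided taken here).

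**Assumed inputs.** Age gap D of 0 to 1.5 within-group SDs; within-group correlation r between age and EMG of 0.3 to 0.4; no true group effect. None of these is in the documents.

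**Step 1: bias and false-positive rate for one EMG level.** With EMG in within-group SD units, the bias in the unadjusted difference is r × D. The noncentrality is r × D × √(15/2) = 2.739 × r × D, on 28 degrees of freedom, with critical value 2.048.

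| Age gap D | Bias r × D | Noncentrality | False-positive rate |
|---|---|---|---|
| 0 | 0 | 0 | 0.050 |
| 0.5 | 0.15–0.20 | 0.41–0.55 | 0.068–0.083 |
| 1.0 | 0.30–0.40 | 0.82–1.10 | 0.125–0.185 |
| 1.5 | 0.45–0.60 | 1.23–1.64 | 0.222–0.355 |

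**Step 2: what the homogeneity test on age can do.** With 15 per group, the power of the t test on age is 26% at a 0.5 SD gap, 75% at 1.0 SD and 98% at 1.5 SD. By simulation, among studies with a false-positive EMG result, the age test is also significant in about 87–90% at 1.0 SD and over 99% at 1.5 SD. Unflagged false positives at 1.0 SD are therefore about 12.5% × 0.13 = 1.6% to 18.5% × 0.10 = 1.9% of all studies. The high rates arise mostly where the imbalance would be seen. What is missing is any rule for what happens next.

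**Step 3: effect of adjustment.** With age as a linear covariate and a linear age effect, the simulated rate returns to about 0.05 at every gap in the table. The cost is precision if ages overlap poorly. At 1.5 SD the mean standard error rises from 0.362 to 0.428–0.446, and 0.428/0.362 = 1.18, 0.446/0.362 = 1.23.

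**Step 4: limb and sex, also on assumed inputs.**
- Limb: if half the operated limbs are non-dominant and dominance is worth 0.2–0.5 SD, the offset is 0.5 × (0.2 to 0.5) = 0.10–0.25 SD, giving a rate of 6–10%.
- Sex: a 30-point difference in sex mix and a sex effect of 0.3–0.5 SD give 0.3 × (0.3 to 0.5) = 0.09–0.15 SD, or 6–7%.

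**Step 5: which contrasts are exposed.** The group difference in level is exposed. The within-patient change is not, because fixed traits cancel. A group-by-task contrast is not exposed if the offset is equal in all three tasks; it is exposed if the age, sex or limb effect differs by task.

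**The case against.** The strongest reply has four parts.

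- **The size is assumed.** This stands. The documents give no expected ages, no sex mix, no age-EMG relation and no direction, and the visible text does not define the EMG metric or its normalisation. A reader might take the upper rates as an estimate of bias in this study; they are not one.
- **The planned tests expose the worst cases.** This largely stands for gaps of 1.0 SD or more, and it would be wrong to call the tests useless. But they detect and do not correct, and no action is attached. At 0.5 SD they miss the gap about three times in four, although the inflation there is small. A difference in baseline EMG may also reflect the diseased knee, so only the age test points clearly to age.
- **The primary use may be task contrasts within a subject.** Section 3 speaks of patterns and 4.2.1 of several tasks in a constant setting. This stands in part: such contrasts are safe under an equal offset. Yet 4.2.1 speaks of intensity, which is a level, and 7.2 plans comparisons between groups.
- **The study is preliminary.** This lowers the stakes, but a preliminary estimate can still be biased.

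A reader might also infer that the evidence on activation after surgery is confounded throughout. The documents do not support that: 7.2 also plans within-group comparisons, and patients have a pre-operative session.

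**Conclusion.** The concern holds for the patient-versus-healthy difference in EMG level, and for group-by-task contrasts only where the age, sex or limb effect varies by task. In the visible text nothing aligns the groups on age or sex, the limb rule differs between them, no covariate is named, and no response to a flagged imbalance is stated. A non-significant homogeneity test with 15 per group is weak reassurance.

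Age leads as a matter of judgement, since patients are TKA candidates and controls are bounded only at 18. The documents do not show that controls will be younger or by how much. Sex and limb are lesser matters under the assumptions used. The finding is a correctable weakness of design and analysis, worth fixing before recruitment, and not evidence that the results will be biased.

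**What to change.** 1. **Sections 5 and 6.1:** state that controls are frequency-matched to patients by age band and sex.
2. **Section 7.2:** state that every patient-versus-healthy contrast includes age and sex as pre-specified covariates, with their interaction with task where group-by-task is tested, whatever the homogeneity tests show. Treat those tests as descriptive.
3. **Data form:** record whether each patient's operated limb is the dominant one, if Attachment B does not already do so, and state limb dominance as a limitation of the group contrast.

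Matching and adjustment belong together. Adjustment alone loses precision when ages overlap poorly and relies on a linear age effect; matching alone leaves residual differences within bands.

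The cost is a narrower choice of the 15 volunteers, which may be harder to fill within July to September, and one data field. Adjustment uses two of the 30 − 2 = 28 between-subject degrees of freedom. If task interactions are fitted to one three-task session, it also uses 2 × 2 = 4 of the 2 × 28 = 56 within-subject ones. If matching fails and the age gap is 1.5 SD, the adjusted standard error for a single level is about 18–23% wider. No visits are added.

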4.2.2 Secondary endpoint

The secondary aim is to understand whether there is a correlation between the acquired surface EMG data and the pain referred by the patient and the patient's functional ability. The secondary outcomes will be the pain referred by the patient and the patient's functional ability. The referred pain will be assessed through the Numeric Rating Scale (NRS) at the beginning of every session. The functional ability will be assessed with the Timed Up and Go Test (TUG) on the third day post-surgery and via a descriptive analysis on the patient's deambulation autonomy, considering the following characteristics: ambulatory aids, need for supervision or assistance, and maximum distance covered.

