7.1 Sample Size

The primary outcome of this study is the EMG signal detected during different isometric contractions of the quadriceps muscle. In the published scientific literature, there is insufficient data to define the minimal statistically significant difference for this outcome. Therefore, it is not possible to calculate the sample size. Some studies exist which compare the muscular activation in the inferior limb between healthy subjects and patients who have undergone PTG, with 10 subjects for each group [13]. In this study, 15 healthy subjects and 15 patients will be recruited; it is estimated that this sample will be enough to obtain a preliminary valuation of the differences between groups.

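### The regression of EMG on pain and function has no patient or session term, although EMG and NRS are recorded at three sessions per patient

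*Combined protocol and SAP*

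**What the plan says.** The secondary aim (section 4.2.2) is whether the EMG data correlate with reported pain and with functional ability. The method, in section 7.2, is "Linear regression will be used to investigate the correlation between the EMG outcomes and the secondary outcomes (NRS and TUG", and "The threshold value for the statistical significance will be fixed at 0.05". The section does not say which variable is dependent, whether sessions are pooled or taken singly, how muscles, tasks and repetitions are summarised, whether controls enter, or how multiple tests are handled. It names a repeated-measures mixed model, but only for differences between and within groups.

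The data structure is in sections 4.2 and 6.1:

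- Sessions: "The assessment sessions will be conducted the day before the operation and on the first and third postoperative day".
- EMG: three muscles and three tasks; "Each task will be repeated twice and the execution order will be randomized".
- NRS: every session. Section 4.2.2 says "The referred pain will be assessed through the Numeric Rating Scale (NRS) at the beginning of every session", while section 6.1 places it after the EMG evaluation.
- TUG: section 4.2.2 gives day 3 only; section 6.1 gives the day before surgery and day 3.
- Controls: "The control group will be exposed once to the same assessments, with the EMG applied on the quadriceps muscle of the dominant limb".

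On numbers, section 7.1 says "In this study, 15 healthy subjects and 15 patients will be recruited".

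**The concern.** Ordinary linear regression assumes independent rows. Three sessions from one patient are unlikely to be independent, so pooling them overstates the information in the data.

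There is also a common cause. The rationale in section 3 expects quadriceps activation to be reduced from day 1, and the background in section 2 counts pain among the symptoms typical of the early postoperative period. If surgery lowers EMG and raises NRS, a pooled slope can be significant when, among patients at the same session, pain says nothing about activation. The study could then report a pain-EMG link that only restates that both changed after surgery.

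Taking one session at a time avoids both problems, but leaves small samples and many tests with no rule for reading them.

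**Working it through.** **Reference value.** There is no power figure to reproduce: section 7.1 states "Therefore, it is not possible to calculate the sample size". The only benchmark is the nominal 0.05, taken as two-sided because sidedness is not stated.

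**Inputs from the documents.** 15 patients; 3 sessions for EMG and NRS; 1 or 2 occasions for TUG; 3 muscles x 3 tasks = 9 EMG series once the two repetitions are averaged.

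**Assumptions (the documents give neither).** ICC of 0 to 0.7, the same for both variables. Shifts in SD units present at both postoperative sessions, EMG down and NRS up.

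**Clustering, by formula.** The design effect for pooled rows without a shift is about 1 + (m - 1) x ICC_x x ICC_y. With m = 3:

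- ICC 0.3: 1 + 2 x 0.09 = 1.18, so 45 rows carry the information of about 38.
- ICC 0.5: 1 + 2 x 0.25 = 1.50, about 30 rows.
- ICC 0.7: 1 + 2 x 0.49 = 1.98, about 23 rows.

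**Common shift, by formula.** With one session before surgery and two after, a shift d adds (1/3)(2/3)d² = 0.222d² to a variable's variance. Shifts of 1 SD in opposite directions add a covariance of -0.222, so the spurious r is about -0.222/1.222 = -0.18. Pooled, |r| above 0.29 is declared significant.

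**Simulated type I error** (15 patients x 3 sessions, no true association at patient level or within patient, 20,000 data sets per cell):

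| Shift in each variable | ICC | Pooled | Session term only | Patient + session | One session |
|---|---|---|---|---|---|
| none | 0 | 0.050 | 0.050 | 0.051 | 0.051 |
| none | 0.3 | 0.069 | 0.071 | 0.049 | 0.051 |
| none | 0.5 | 0.106 | 0.105 | 0.048 | 0.047 |
| none | 0.7 | 0.170 | 0.167 | 0.049 | 0.052 |
| 0.5 SD | 0.5 | 0.115 | 0.107 | 0.053 | 0.051 |
| 1 SD | 0 | 0.231 | 0.051 | 0.052 | 0.054 |
| 1 SD | 0.5 | 0.271 | 0.107 | 0.049 | 0.050 |

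Further runs at ICC 0.5 with unequal shifts gave 14% (EMG down 0.5 SD, NRS up 1 SD); repeat runs with 1 SD in both gave 27% to 28%. A session term alone removes the shift bias but not the clustering. Patient and session terms together remove both.

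**TUG.** If two occasions are pooled, the rates with no shift are 0.06, 0.08 and 0.11 at ICC 0.3, 0.5 and 0.7. With 1 SD shifts they are 0.20, 0.21 and 0.24. With day 3 only there is one row per patient and no inflation.

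**One session at a time.** NRS: 9 x 3 = 27 tests. TUG: 9 x 1 = 9 or 9 x 2 = 18. The total is 36 or 45. If every null were true, the expected false positives would be 36 x 0.05 = 1.8 or 45 x 0.05 = 2.25, whatever the correlation among tests. At n = 15, significance needs |r| above 0.51, and 80% power needs a true r of about 0.67.

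**Is a random intercept enough?** No. A random patient intercept with raw NRS mixes the within- and between-patient slopes. A small simulation (400 runs, some with convergence warnings; ICC 0.5, zero within-patient relation, assumed between-patient correlation of -0.8) gave a mean slope of -0.23 and about 31% rejections. Fixed patient effects gave a slope of about 0 and 5% rejections.

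**The case against.** The strongest reply is that the plan never says sessions will be pooled. That stands. A reader might infer that the secondary p-values are simply wrong, but the sentence in section 7.2 is equally met by one regression per session, and each of those tests holds its 5% level. What the documents show is an unspecified analysis that permits an invalid version, not a planned error.

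Four other stronger readings also go too far:

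- The count of 36 or 45 tests might be taken as a failure of independence. It is a multiplicity matter, and it is a maximum: it assumes that all nine series are tested at every session.
- One might say that within-patient change is the question asked. Sections 4.1 and 4.2.2 ask only about correlation, and a between-patient correlation fits that wording.
- The three-session argument might be applied to TUG. TUG has one or two occasions, depending on the section.
- Larger shifts give larger figures: about 55% at ICC 0.5 with EMG down 1 SD and NRS up 2 SD. Nothing in the documents supports a 2 SD rise in pain.

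It is also fair to say that this is a secondary aim in a study that section 7.1 calls preliminary. That limits the stakes but does not settle which analysis will be run.

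**Conclusion.** The point holds as an under-specification with a material risk. For NRS, the stated method has no term for the repeated sessions, and neither way of applying it serves the secondary aim well. Pooling gives roughly 7% to 17% false positives from clustering alone at ICC 0.3 to 0.7. At ICC 0.5 the rate is 14% to 28% when surgery also shifts EMG by 0.5 to 1 SD and NRS by 1 SD. Session-by-session analysis is valid test by test, but weak and unadjusted. All the inflation figures rest on assumed ICCs and shifts. The direction of the shifts is plausible from the protocol's own rationale; their size is not given. Because the choice is left open, it could also be made after the data are seen.

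**What to change.** Replace the regression sentence in section 7.2 with text to this effect:

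- **NRS, patients only.** For each muscle and task, regress EMG (mean of the two repetitions) on NRS in a repeated-measures model with session as a fixed factor. Either fit patient as a fixed effect, or use a random patient intercept with NRS split into the patient's mean and the deviation from it. The within-patient slope is then kept apart from between-patient differences. A random intercept with unsplit NRS is not sufficient.
- **TUG.** Ordinary regression with one row per patient, using day 3, the occasion common to both sections.
- **Multiplicity.** State an adjustment across the nine muscle-task series (Holm would do), or label these analyses exploratory.
- **Reconcile** sections 4.2.2 and 6.1 on the TUG occasions and on whether NRS precedes or follows the EMG session.

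The session factor removes the average perioperative change from the NRS slope. That change remains the subject of the repeated-measures ANOVA already planned.

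The cost is a few lines of text. SPSS 20 has the MIXED procedure, and no new data are needed. The price is residual degrees of freedom: with fixed patient effects, 45 - 15 - 3 = 27, against 45 - 2 = 43 for a pooled regression.

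### The EMG–pain and EMG–function regressions are all judged at 0.05 with no key regression, adjustment or exploratory label; labelling them exploratory is a cheap improvement

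*Combined protocol and SAP*

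**What the plan says.** Section 4.1 sets the secondary question broadly: "it will be investigated whether any correlation exists between the outcomes obtained, the pain reported by the patient and his or her functional ability". Section 4.2.2 repeats it: "The secondary aim is to understand whether there is a correlation between the acquired surface EMG data and the pain referred by the patient", and extends it to functional ability.

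The analysis is one sentence in section 7.2: "Linear regression will be used to investigate the correlation between the EMG outcomes and the secondary outcomes (NRS and TUG". The only decision rule follows shortly after: "The threshold value for the statistical significance will be fixed at 0.05".

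The EMG outcomes are plural. Section 4.2.1 covers three muscles: "more specifically of the vastus medialis, lateralis and rectus femoris muscles, by means of electromyographic signal acquisition". Section 6.1 has each subject perform three isometric tasks (knee extension, hip flexion, and hip flexion combined with extension of the opposite hip). On timing, section 6.1 says: "The assessment sessions will be conducted the day before the operation and on the first and third postoperative day". It also says: "The NRS scale will be administered to the patients after each quadriceps evaluation session". TUG is placed on day 3 in section 4.2.2, but on both the preoperative day and day 3 in section 6.1.

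The plan does not say which muscle, task, EMG summary or session enters the regressions, or how many regressions there are. The word preliminary occurs in section 7.1, where it describes the differences between groups. The post hoc sentence in 7.2 follows the repeated-measures ANOVA and names no correction.

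**The concern.** A question of the form *does any correlation exist* can be answered yes by one small p-value out of many. With one unadjusted threshold, and no statement of which regression carries the secondary aim, the chance of a spurious yes grows with the number of regressions.

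The sample adds to this. In a single-session regression on 15 patients, only a large observed correlation can reach p<0.05. A false positive picked from the set would therefore look strong on paper. Section 13 plans a journal manuscript, so a reader could meet such a correlation without knowing how many were tried.

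This is separate from the group and session comparisons of the primary outcome. Naming a single EMG outcome would shrink the problem but not remove it, because two to five regressions would remain.

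**Working it through.** The plan states no number of regressions, power or family-wise error, so there is no figure of its own to reproduce.

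**Inputs from the documents**
- Muscles: 3 (4.2.1). Tasks: 3 (4.2.1, 6.1). EMG outcomes per session: 3 × 3 = 9.
- NRS occasions: 3 (6.1).
- TUG occasions: 1 (4.2.2) or 2 (6.1).
- Patients: 15 (7.1). Threshold: 0.05 (7.2).

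**Assumptions**
- Two-sided tests; the plan does not state sidedness.
- Patients only, one predictor per regression, one session per regression.
- No true association anywhere.
- A common correlation ρ among EMG outcomes within and across sessions, and among the NRS and TUG measures. The documents give no value, so a range is shown.

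**Count**
- TUG on day 3 only: 9 × 3 + 9 × 1 = 36.
- TUG also before surgery: 9 × 3 + 9 × 2 = 45.
- Day 3 only, NRS and TUG: 9 × 2 = 18.
- One EMG outcome: 2 (day 3), 4 (NRS at three sessions, TUG once) or 5 (TUG twice).

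**Expected false positives**, whatever the correlation: 36 × 0.05 = 1.8; 45 × 0.05 = 2.25.

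**Chance of at least one p<0.05.** If the tests were independent, this is 1 − 0.95^k. With correlation it was simulated at n = 15.

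| Reading | k | Independent | ρ = 0.5 | ρ = 0.8 |
|---|---|---|---|---|
| All sessions, TUG twice | 45 | 0.90 | 0.76 to 0.77 | about 0.45 |
| All sessions, TUG day 3 | 36 | 0.84 | 0.70 | 0.37 to 0.41 |
| Day 3 only | 18 | 0.60 | 0.46 | 0.27 |

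Where a cell shows a range, separate simulation runs differed by that much.

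With a single EMG outcome, the chance is about 0.07 (two regressions, ρ = 0.9) to about 0.18 (four regressions). Five regressions give 0.21 at ρ = 0.5, with an independence value of 1 − 0.95^5 = 0.23.

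**Size of correlation needed.** The critical value is |r| = t / √(n − 2 + t²).
- n = 15, two-sided 0.05: t = 2.160 on 13 df, so |r| = 2.160 / √(13 + 4.666) = 0.51.
- n = 15, two-sided 0.025 (Holm's first step for two tests): t = 2.533, so |r| = 2.533 / √(13 + 6.416) = 0.57.
- n = 30, two-sided 0.05: t = 2.048 on 28 df, so |r| = 2.048 / √(28 + 4.194) = 0.36.

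**Power at n = 15** for an assumed true r of 0.5 (simulated): about 50% at 0.05 and about 38% at 0.025.

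**The case against.** The strongest reply is proportionality. This is a secondary aim in a 15-patient observational study that says no sample size can be calculated and calls its main comparison preliminary. It would be odd to read the secondary correlations as more confirmatory than the primary comparison. No passage says that a single p<0.05 settles the question, and much of the inflation comes from the undefined EMG outcome rather than from the regressions themselves. All of this stands, and it is why the point is a cheap improvement and no more. It does not remove the gap, because the plan fixes a significance threshold and never calls these regressions exploratory.

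A reader might infer stronger claims that the documents do not support:

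- *A false positive is more likely than not.* This depends on an assumed family, correlation and global null. It fails for 36 or 45 regressions at correlation 0.8, and for day 3 only at 0.5. Section 2 also reports that experimentally induced pain produces a quadriceps recruitment deficit, which argues against a global null for EMG and pain.
- *Any significant correlation must have |r| of at least 0.51.* This holds only for single-session regressions in 15 patients. Section 7.2 does not restrict the regressions to patients, and at n = 30 the bound is 0.36.
- *The correlations are meant to direct physiotherapy.* Section 3 says only that the results could be useful. The firmer wording under Ethical considerations in the opening summary is about how the quadriceps activates, not about these correlations.

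**Conclusion.** The point holds as a cheap improvement. The plan asks an open question, implies many regressions and applies 0.05 to them without a key regression, adjustment or exploratory label. Every reading examined that has more than one regression carries an error above the nominal 5%, from about 7% for two regressions on one EMG outcome to about 76% for the full set of 45 at correlation 0.5.

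The direction is secure. The size is not, because the number of regressions and the correlations are assumptions and the percentages describe the case of no true association. The 4.2.2 and 6.1 difference on TUG moves the count between 36 and 45 without changing the conclusion. What is at stake is how a reported correlation may be described, not the validity of the primary comparison.

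**What to change.** In section 7.2, state that the EMG–NRS and EMG–TUG regressions are exploratory, that all of them will be reported as r or slope with 95% CI, and that p<0.05 will not be used to claim that a correlation exists. This takes two or three sentences and no new data or patients.

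Optionally, if the sponsor wants a formal secondary conclusion, pre-name one EMG–NRS and one EMG–TUG regression, each with one EMG summary at one session. Test the two with Holm at 0.05 overall and keep the rest exploratory. This option also needs the NRS timing settled, since 4.2.2 places it at the start of each session and 6.1 after the quadriceps evaluation.

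The cost is that no correlation outside a pre-named pair can be called significant. With Holm, the smaller p-value must also be below 0.025, which needs |r| of about 0.57 instead of 0.51 and lowers power for an assumed true r of 0.5 from about 50% to 38%. For that reason the exploratory label alone is sufficient.
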